18.10 Analyses of Extension Phase Data

Data from part 1 of the Extension Phase

*The main objective of part 1 of the Extension Phase is to investigate the safety and efficacy of every 7 day dosing by evaluating ABR for this dosing regimen and comparing it to the same historical bleeding episode rates as used in the primary analysis for the co-primary efficacy endpoint in the Main Phase. Prophylactic effect of every 7 day dosing will be concluded if the bleeding rate is significantly below 50% of the historical on-demand bleeding rate (i.e. significantly lower than 12) as well as within 25% of the historical prophylaxis bleeding rates (i.e. significantly lower than $6.8 * 1.25 = 8.5$). Since both must be met in practice it must be shown that the bleeding rate is significantly lower than 8.5.*

An analysis similar to that for the co-primary endpoint in the Main Phase will be carried out for the bleeding episodes in the two randomised treatment regimens during the Extension Phase part 1, adding treatment regimen as a factor to the model. Subjects switching from the every 7 day dosing arm to the non-randomised every 4 day dosing arm will be handled as withdrawals in this analysis. The imputation for withdrawals will be similar to that for the Main Phase, except that planned maximum duration is now 6 months.

Estimates of the annualised bleeding rates for each randomised regimen will be provided with 95% confidence intervals. Prophylactic effect of every 7 day dosing will be concluded if the upper limit of the 95% CI is below 8.5. In addition, the two randomised treatment regimens will be compared by reporting the estimated ratio between the two randomised treatment regimens with corresponding 95% confidence interval.

As for the co-primary endpoint in the Main Phase, a sensitivity analysis will be carried out where bleeding episodes for withdrawals are not imputed.

ABR based on accumulated number of bleeding episodes (Main Phase + Extension Phase part 1) will be evaluated for the every 4 day dosing regimens combined, i.e., combining the randomised and non-randomised arm. The model used will be the same as for the primary analysis of the Main Phase data.

Only treatment requiring bleeding episodes will be considered in the above evaluations of ABR

Incidence rate of FVIII-inhibitor and haemostatic effect of N8-GP when used for treatment of bleeding episodes will be evaluated based on accumulated data (Main Phase + Extension Phase part 1).

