5.3.1 Prophylaxis

...

Other changes of the dose or dosing interval for prophylaxis are not allowed within *the main phase of the trial*. However, extra doses of N8-GP will be administered if a patient experiences a treatment requiring bleeding episode or in case of minor surgery.

Extension Phase part 1: The prophylaxis dose of N8-GP is administered in the non-randomised group every 4 days or in the randomised group every 4 day or every 7 day depending on which treatment arm the patient is allocated to. Based on the bleeding pattern, the Investigator may change the every 7 day prophylaxis treatment to an every 4 day treatment regimen (the non-randomised arm) *at any time*. ~~but~~ Changing vice versa is not permitted. *In addition the Investigator must monitor the patient on an on going basis and change patients from every 7 day prophylaxis treatment to an every 4 day treatment regimen in accordance with the following rule. A patient on every 7 day prophylaxis must be switched back to every 4 day prophylaxis if either of the following criteria are met over a 8 week period:*

- *Two or more spontaneous bleeding episodes*
- *One severe bleeding episode requiring hospitalisation.*

Novo Nordisk will monitor that patients are switched from the every 7 day prophylaxis treatment to an every 4 day treatment regimen adhering to the rule mentioned above. Novo Nordisk will furthermore monitor the number of patients switching from every 7 day to every 4 day treatment regimen and will terminate the 7 day treatment arm if the below rule is met:

- *If at least 15 out of 30 patients (or 50% of 30 or more) whom have been randomised to the every 7 day treatment arm are switched back to the every 4 day treatment arm, then the every 7 day treatment arm will be closed and all remaining patients will be switched to every 4 day treatment.*

...

Extension Phase part 2: During this period it is possible to ~~adjust~~*change* the prophylaxis treatment of patients to *every 4 day or 7 day treatment*~~an individualised regimen. Treatment regimens ranging from once weekly to every 4 day will be allowed: every 4 day, every 5 day, every 6 day or every 7 day.~~ For deciding to change a regimen it is strongly recommended to follow *the Investigator must monitor the patient on an on going basis and follow the below* ~~guidelines~~*rules for change of regimen:*

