8.1.7 Transfer of Patients to pathfinder™3 due to Major Surgeries

...

Upon completion of pathfinder™3, patients may return to pathfinder™2, re-entering the prophylactic or on-demand treatment arm as per their prior participation in the trial. *Randomised patients in extension part 1 on every 4 or 7 day prophylaxis treatment regimen must return to the non-randomised every 4 days prophylaxis treatment regimen*

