2.2 Statistical Methods

2.2.1 General Considerations

Novo Nordisk A/S will be responsible for the statistical analysis. All tests will be performed as 1-sided tests on 2.5% significance level. All bleeding endpoints will be evaluated based on bleeding episodes requiring treatment with N8-GP. Non-treatment requiring bleeding episodes that coincide with regular prophylaxis doses are not included in the analyses.

Multiple bleeding locations occurring from the same event (e.g. due to a bicycle accident) or at the same time point will be counted as one bleeding episode and only one haemostatic response will be considered for the bleeding episode. In case different responses were registered for different bleeding locations in such a bleeding episode, the worst response will be used in the analysis. As stated in the protocol, a re-bleed is defined as a worsening of symptoms in the same location after an initial period of improvement, either on treatment or within 72 hours after stopping treatment. If a bleed occurs in the same location later than 72 hours after stopping the treatment it is

considered a new bleed. Re-bleeds will only be considered for joint bleeds since the specific location for other bleeds e.g. in subcutaneous are not captured in the database.

In the sub analyses of annualised bleeding rate where there are less than 5 patients in a sub-group, model based estimation will not be done. If no bleedings occur in a sub-group, then the confidence interval will not be calculated.

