For patients who were withdrawn in the Pivotal part the planned exposure time will be until the end of the pivotal part as described above. For patients who were withdrawn in the main part after the pivotal part ended, the maximum expected exposure time will be used, i.e. 100 weeks as this is the maximum duration for main phase. For patients withdrawn during extension phase part 1, the planned exposure is 24 weeks (duration of extension phase part 1) added to the actual exposure in main

For calculations only including the randomised period, the planned exposure time will be the time from visit 14 to visit 17, i.e. 24 weeks. Patients that change from Q7D to non-randomised part of Q4D will have their bleeds imputed using a planned exposure time of 24 weeks using the same approach as in the pivotal part of the trial even though they are not withdrawn from the study. This is to avoid bias for randomized Q7D caused by patients withdrawing due to high bleeding rate.

Calculations of ABR for extension phase part 2:

For patients withdrawn prior to extension phase part 2, planned exposure is calculated as explained above. For patients withdrawing during extension phase part 2, planned exposure in extension phase part 2 will be calculated using the overall cut-date (15Aug2017) as planned end date. The actual exposure time in main and extension phase part 1 is added to the planned exposure time in extension phase part 2, to get the overall planned exposure time for a withdrawn patient.

Planned exposure time is only relevant for the treatment regimen the patient is on, when being withdrawn. Time on other regimens and time in surgery trial is subtracted when calculating planned exposure time.

For patients who withdrew within 1 month, imputation will be conducted by assuming an annualised bleeding rate of 24 (bleeds per year) for the missing period. This also applies to change from Q7D to Q4D in the randomised part of extension phase part 1.

Estimates of the annualised bleeding rates for each regimen will be provided together with the 95% confidence intervals as described in the protocol.

Sensitivity analyses:

Analysis applying a different model

A sensitivity analysis based on a negative binomial regression model with number of bleeding episodes requiring treatment as the outcome variable, and adjusting for exposure time will be performed.

Analysis without imputation to planned trial duration

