2.10 Analyses of Extension Phase Data

Data from part 1 of the Extension Phase

The main objective of part 1 of the Extension Phase is to investigate the safety and efficacy of every 7 day dosing by evaluating ABR for this dosing regimen and comparing it to the same historical bleeding episode rates as used in the primary analysis for the co-primary efficacy endpoint in the Main Phase. Prophylactic effect of every 7 day dosing will be concluded if the bleeding rate is significantly below 50% of the historical on-demand bleeding rate (i.e. significantly lower than 12) as well as within 25% of the historical prophylaxis bleeding rates (i.e. significantly lower than $6.8 \times 1.25 = 8.5$). Since both must be met in practice it must be shown that the bleeding rate is significantly lower than 8.5.

An analysis similar to that for the co-primary endpoint in the Main Phase will be carried out for the bleeding episodes in the two randomised treatment regimens during the Extension Phase part 1, adding treatment regimen as a factor to the model. Subjects switching from the every 7 day dosing arm to the non-randomised every 4 day dosing arm will be handled as withdrawals in this analysis.

The imputation for withdrawals will be similar to that for the Main Phase, except that planned maximum duration is now 6 months.

Estimates of the annualised bleeding rates for each randomised regimen will be provided with 95% confidence intervals. Prophylactic effect of every 7 day dosing will be concluded if the upper limit of the 95% confidence intervals (CI) is below 8.5. In addition, the two randomised treatment regimens will be compared by reporting the estimated ratio between the two randomised treatment regimens with corresponding 95% confidence interval.

As for the co-primary endpoint in the Main Phase, a sensitivity analysis will be carried out where bleeding episodes for withdrawals are not imputed.

ABR based on accumulated number of bleeding episodes (Main Phase + Extension Phase part 1) will be evaluated for the every 4 day dosing regimens combined, i.e., combining the randomised and non-randomised arm. The model used will be the same as for the primary analysis of the Main Phase data.

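### Surgical exits from the randomised part have an imputation rule in the every-7-day arm only, and a first-month exit there would be counted at 24 bleeds per year

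*SAP*

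**What the plan says.** Protocol 8.1.7, in the amendment of 29 November 2013 (number 18 in the SAP's list), adds for surgery: "Randomised patients in extension part 1 on every 4 or 7 day prophylaxis treatment regimen must return to the non-randomised every 4 days" regimen. The exit is forced, and it is the same in both arms.

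The analysis text names one arm. Protocol 18.10 says: "Subjects switching from the every 7 day dosing arm to the non-randomised every 4 day dosing arm will be handled as withdrawals", and SAP 2.10 repeats it. SAP 2.2.2 adds: "Patients that change from Q7D to non-randomised part of Q4D will have their bleeds imputed using a planned exposure time of 24 weeks". The reason it gives is to avoid bias from patients leaving Q7D because they bleed a lot. For withdrawals within one month the missing period is filled at 24 bleeds per year, and "This also applies to change from Q7D to Q4D in the randomised part of extension phase part 1". After one month the patient's own observed rate is carried forward.

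The same part of SAP 2.2.2 says that time in the surgery trial and time on other regimens is subtracted from planned exposure. It does not say how this fits with the fixed 24 weeks.

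For success, SAP 2.10 says: "Prophylactic effect of every 7 day dosing will be concluded if the upper limit of the 95% confidence intervals (CI) is below 8.5". The Q7D/Q4D ratio is reported with a 95% confidence interval and has no success rule. A sensitivity analysis without imputation is planned.

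Protocol 5.3.1 has a rule on when the Q7D arm closes: if at least 15 of 30 patients (or half of a larger number) "are switched back to the every 4 day treatment arm, then the every 7 day treatment arm will be closed".

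**The concern.** The imputation was designed for exits driven by bleeding. A return from surgery is forced by the protocol, so it lies outside that purpose but inside the wording. A Q7D patient who returns from surgery to Q4D has changed from Q7D to non-randomised Q4D and is imputed. A randomised Q4D patient who returns from surgery keeps his regimen and leaves only the randomised group, and no sentence says how he is analysed. An analyst who follows the text literally imputes in one arm and not in the other for the same event.

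The main thing at stake is the Q7D/Q4D ratio, the only randomised comparison in the trial. The shift in the Q7D rate itself is the same in relative terms, but it matters less because that rate is judged against 8.5. A side issue is that the closing count in 5.3.1 does not say whether surgical returns under 8.1.7 are included.

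**Working it through.** **The plan's own use of the 24-per-year rule.** Protocol 18.1 assumes one first-month withdrawal among 120 patients, which lifts the annualised bleeding rate (ABR) by 24/120 = 0.2, from 6.8 to 7.0. With over-dispersion 5 and limit 8.5, power = Φ((8.5 − 7.0)/√(7.0 × 5/120) − 1.96) = Φ(2.78 − 1.96) = 79.3%, against 79% stated. By the same shortcut, one such patient in an arm of 30 adds 24/30 = 0.8. The exact figure below is a little smaller.

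**Inputs.** From the documents: 24-week period; 24 bleeds per year within one month; own rate afterwards; 2:1 randomisation to Q7D and Q4D; entry with 0–2 bleeds in 180 days, so about 0–4 per year. Assumed, because no size is stated for the randomised part: 20, 30 or 40 Q7D patients (30 is the number in the closing rule), true ABR λ equal in both arms, and surgery unrelated to bleeding.

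**First-month exit.** With n Q7D patients, one leaving at week w, the Poisson estimate is total bleeds over total exposure:

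rate = [(n − 1)·λ·24/52 + λ·w/52 + 24·(24 − w)/52] ÷ (n·24/52)

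For n = 30, λ = 2, w = 4: (26.77 + 0.15 + 9.23) ÷ 13.85 = 36.15 ÷ 13.85 = 2.61.

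| Q7D patients | true ABR | exit week | Q7D rate | ratio to Q4D |
|---|---|---|---|---|
| 30 | 1 | 2 | 1.70 | 1.70 |
| 30 | 2 | 2 | 2.67 | 1.34 |
| 30 | 2 | 4 | 2.61 | 1.31 |
| 30 | 3 | 4 | 3.58 | 1.19 |
| 30 | 4 | 2 | 4.61 | 1.15 |
| 20 | 2 | 4 | 2.92 | 1.46 |
| 40 | 2 | 4 | 2.46 | 1.23 |

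Over the imputed 20 weeks the patient would be expected to have 2 × 20/52 = 0.8 bleeds at ABR 2; he is given 9.2.

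**Later exit.** Carrying the own rate forward gives expected bleeds (λ·w/52) × (24/w) = λ·24/52, the same as for a patient who stays. A simulation of exits at weeks 8, 12 and 16 agrees: the mean Q7D rate is 1.993–2.007 when the true ABR is 2. There is no shift, only slightly more variance.

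**If surgery time is subtracted.** With S weeks in the surgery trial, the imputed bleeds become 24 × (20 − S)/52. For S = 8 (assumed) that is 5.5, and the rate for n = 30 and λ = 2 is (26.77 + 0.15 + 5.54) ÷ (712/52) = 32.46 ÷ 13.69 = 2.37. If time on Q4D were also subtracted, as the sentence literally says, nothing would be left to impute for any switcher, which contradicts the explicit switch rule. The sentence therefore cannot apply in full to the randomised part, and the SAP does not say which part does.

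**Against 8.5.** I simulated 20,000 trials with 30 Q7D and 15 Q4D patients, gamma-distributed patient rates (shape 1, assumed) and a common Pearson scale. One exit at week 4 moves the mean upper 95% limit from 3.31 to 4.55 at ABR 2 (over-dispersion from about 1.8 to 2.9), and from 6.18 to 7.04 at ABR 4. At ABR 2 the limit stays below 8.5 in practically every run even with three exits. At ABR 4, the top of the entry range, the share of runs below 8.5 is 96% with no exit, 89% with one and 51% with three.

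**One common rule.** With observed data only in both arms, or with the same imputation in both arms and the same share of exits, the expected ratio is 1.00.

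**The case against.** The strongest points on the other side are these.

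- **Most exits are not counted as failures.** A reader might infer that every surgical exit from Q7D is treated as a treatment failure. The documents do not support this: the 24-per-year value is limited to one month, and later exits keep the patient's own rate. This stands, and it confines the bias to first-month exits. The documents do not show that any occurred.
- **The Q4D side is silence.** A reader might also infer that the plan sets a contrary rule for Q4D. It does not. The general imputation for premature withdrawal could be stretched to a Q4D patient leaving the randomised part. But he is not withdrawn from the trial, whereas for Q7D the SAP says explicitly that switchers are imputed although still in the study.
- **Timing is unclear.** The regimen change happens on return from surgery, so departure at week 4 need not be a change within the first month, and surgery time may come off. Both would reduce the effect. Neither reading is settled in the text.
- **Sensitivity analyses exist.** SAP 2.10 plans a part 1 analysis without imputation, and SAP 2.2.2 lists one that drops only the first-month imputation. They would show that something had moved. They also remove the imputation for early switches driven by bleeding, so they cannot isolate surgery, and they do not replace the primary ratio.
- **The error is conservative, and part 1 is already reported.** It works against Q7D, the regimen that has to show effect. A change made now favours Q7D after the fact. This is a good reason to report any correction as supplementary.

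**Conclusion.** The point holds in a limited form. Both randomised arms are forced out by surgery, the withdrawal imputation is written for Q7D only, and surgery is not excepted. The resulting bias needs at least one Q7D surgical exit that counts as falling within the first month. Given one, with 30 Q7D patients and equal true rates, the ratio becomes 1.70, 1.34 or 1.15 at an ABR of 1, 2 or 4 (exit at week 2) instead of 1.00. These figures rest on the assumed arm size and rates, on no subtraction of surgery time, and on surgery being unrelated to bleeding, which the documents do not state.

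A reader might go further and infer that the conclusion on Q7D against 8.5 is unsafe. The documents do not support that: with 30 Q7D patients the point estimate reaches 8.5 only with about 8 to 11 first-month exits, and one exit leaves the mean upper limit below 8.5 throughout the entry range. Only several such exits at a rate near 4 per year would put it in doubt. Whether surgical returns belong in the 5.3.1 closing count is an ambiguity of wording with no bearing on the estimate.

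**What to change.** In SAP 2.2.2 and 2.10 and Protocol 18.10, state one rule for transfer to surgery in both randomised arms: count observed bleeds and observed time on the randomised regimen up to transfer, with no imputation. Keep the withdrawal imputation, including 24 per year within one month, for all other Q7D-to-Q4D changes. Say whether the sentence on subtracting surgery time and time on other regimens applies to the randomised part, and how it fits with the fixed 24 weeks.

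The SAP is dated January 2019, after the part 1 reporting. So first check whether any randomised patient left for surgery, and when. If a first-month Q7D exit exists, give the ratio under the common rule as a supplementary analysis beside the reported one. If none exists, say so in a sentence.

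Protocol 5.3.1 and 8.1.7 should be reconciled on whether surgical returns count in the closing rule.

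The cost is about one sentence in each place. The reason for a regimen change is already recorded under Protocol 8.1.4. The downside is slightly less exposure in the estimates.

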2.2.3 Confirmatory Secondary Endpoints

Haemostatic effect of N8-GP when used for treatment of bleeding episodes, assessed on a four-point scale for haemostatic response (excellent, good, moderate and none) by counting excellent and good as success and moderate and none as failure.

In order to protect against false significances this endpoint will only be analysed as a confirmatory secondary endpoint in the pivotal part if the analyses of the co-primary endpoints are both successful. Otherwise this endpoint will be analysed only as a supportive secondary endpoint.

This is assessed as success/failure based on a four-point scale for haemostatic response (excellent, good, moderate and none). Excellent and good counts as success and moderate and none as failure. In addition any bleeding episodes with missing response information will be counted as failures. A success rate of 80% is considered the goal. Due to variation it is not certain that N8-GP will achieve an observed 80% success rate in this trial even if the true success rate is 80%. For that reason it will be demonstrated that the success rate for N8-GP is at most 15% (absolute) worse than 80%.

Let R be the true success rate. The null-hypothesis will be tested against the alternative hypothesis as given by:

$H_0: R \leq 65\%$ against $H_A: R > 65\%$

Specifically this will be done by a logistic regression. The analysis will be performed by use of Proc Genmod in SAS. Correlation within patients will be taken into account using a Generalized Estimation Equations approach with a working correlation matrix with a compound symmetry structure. Adequate efficacy will be concluded if the 1-sided lower 97.5% confidence limit for the success rate is above 65%.

Response as measured by the four point scale will also be summarised and listed. Bleeding episodes will come both from the on-demand periods and from prophylaxis periods. This will be analysed together in the statistical analysis but will also be summarised by treatment regimen.

Sensitivity analyses

Analysis on observed responses only (i.e. excluding missing observations)

A sensitivity analysis will be performed similar to the primary analysis but only analysing bleeding episodes with recorded responses (i.e. not counting any bleeding episodes with missing response as failures).

Analysis imputing missing haemostatic response based on number of infusions used

A sensitivity analysis will be performed using the number of infusions given to impute the haemostatic response for missing data. Specifically missing responses where only 1 dose was used will be counted as success while missing responses where 2 doses were used will be counted as failures.

Analysis imputing missing haemostatic response based on patients recorded responses on other bleeding episodes

A sensitivity analysis will be performed where missing treatment responses will be imputed based on recorded treatment responses from that particular patients. The imputation will be done randomly based on the recorded success rate. As an example if a patient has 2 missing responses and 4 treatment successes in 5 treated bleeds with recorded response then the missing responses will be imputed randomly based on an 80% success chance. Patients with missing responses for all treated bleeding episodes will be imputed as failures for all episodes.

